#### **5.1.2 Hypotheses and Statistical Methods for Secondary Objectives**

##### **5.1.2.1 Hypotheses**

###### ***Non-inferiority on Cervarix***

The objective is to demonstrate that the humoral immune response (in terms of seroconversion) to Cervarix after concomitant administration with CYD dengue vaccine is non-inferior to sequential administration with CYD dengue vaccine measured 28 days after the last dose of Cervarix.

A non-inferiority testing approach will be used to compare seroconversion rates for the 2 antigens (HPV-16 and HPV-18) 28 days after the last dose of Cervarix.

The individual tested hypotheses for the antigen “i” will be as follows:

$$H_0^i: P_{Group1}^i - P_{Group2}^i \leq -\delta$$

$$H_1^i: P_{Group1}^i - P_{Group2}^i > -\delta$$

where the non-inferiority limit  $\delta$  is set at 5% for each antigen “i”.

#### ***Non-inferiority on CYD dengue vaccine***

No statistical hypothesis will be tested on CYD dengue vaccine for secondary objectives.

#### **5.1.2.2 Statistical Methods**

##### ***Non-inferiority on Cervarix***

Non-inferiority for antigen “i” will be demonstrated if the lower bound of the 2-sided 95% CI is greater than  $-\delta$ .

The non-inferiority test will be performed using the 95% 2-sided CI of the difference between groups ( $\alpha=2.5\%$  one-sided). The 95% CI will be calculated based on the Wilson score method without continuity correction as quoted by Newcombe for seroconversion rates.

##### ***Descriptive analysis on Cervarix and CYD dengue vaccine immunogenicity***

No hypotheses will be tested.

Immunogenicity point estimates and their 95% CI will be presented for each and any group, at baseline and after each dose of Cervarix and CYD dengue vaccine.

A complementary analysis on CYD dengue vaccine immunogenicity after each dose will be conducted for each and any group according to the dengue status at baseline (dengue immune, dengue non-immune, and all subjects).

The 95% CIs will be calculated using:

- The normal approximate method for GMs and GMTRs  
Assuming that  $\text{Log}_{10}$  transformation of the titers / data follows a normal distribution, at first, the mean and the 95% CI will be calculated on  $\text{Log}_{10}$  (titers / data) using the usual calculation for normal distribution (using Student’s t distribution with  $n-1$  degree of freedom), then antilog transformations will be applied to the results of calculations, in order to provide geometric means (GMs) and their 95% CI.
- The exact binomial distribution for single proportions (Clopper-Pearson’s method, quoted by Newcombe)

##### ***Safety***

All analyses will be descriptive; no hypotheses will be tested. Safety will be assessed for all subjects and for immune subjects after each and any dose of Cervarix and CYD Dengue vaccine. Moreover, a complementary analysis will be performed for each dose of CYD dengue vaccine, for each and any group, on non-immune subjects.

As there are differences in the intensity considered for measurable reactions depending on ages of subjects, a complementary analysis will be performed according to the following age groups: 9-11 years and 12 to 14 years.

For the main parameters, 95% CIs of point estimates will be calculated using the normal approximation for quantitative data and the exact binomial distribution (Clopper-Pearson method, quoted by Newcombe) for single proportions.

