Table 9.1: Solicited injection site reactions: terminology, definitions, and intensity scales for Subjects aged 9 to 11 Years

CRF term (MedDRA lowest level term [LLT])	Injection site pain	Injection site erythema	Injection site swelling
Diary card term	Pain	Redness	Swelling
Definition		Presence of a redness including the approximate point of needle entry	Swelling at or near the injection site Swelling or edema is caused by a fluid infiltration in tissue or cavity and, depending on the space available for the fluid to disperse, swelling may be either soft (typically) or firm (less typical) to touch and thus can be best described by looking at the size of the swelling
Intensity scale*	Grade 1: Easily tolerated Grade 2: Sufficiently discomforting to interfere with normal behavior or activities Grade 3: Incapacitating, unable to perform usual activities	Grade 1: > 0 to < 25 mm Grade 2: ≥ 25 to < 50 mm Grade 3: ≥ 50 mm	Grade 1: > 0 to < 25 mm Grade 2: ≥ 25 to < 50 mm Grade 3: ≥ 50 mm

* For the subjective reaction of pain, subjects or parents / legally acceptable representatives will record the intensity level (Grade 1, 2, or 3) in the DC. For the measurable reactions of redness and swelling, they will record just the size of the reaction, and the classification as Grade 1, 2, or 3 will be assigned at the time of the statistical analysis.

Table 9.2: Solicited injection site reactions: terminology, definitions, and intensity scales for Subjects aged ≥ 12 Years

CRF term (MedDRA lowest level term [LLT])	Injection site pain	Injection site erythema	Injection site swelling
DC term	Pain	Redness	Swelling
Definition		Presence of a redness including the approximate point of needle entry	Swelling at or near the injection site Swelling or edema is caused by a fluid infiltration in tissue or cavity and, depending on the space available for the fluid to disperse, swelling may be either soft (typically) or firm (less typical) to touch and thus can be best described by looking at the size of the swelling
Intensity scale*	Grade 1: No interference with activity Grade 2: Some interference with activity Grade 3: Significant; prevents daily activity	Grade 1: ≥ 25 to ≤ 50 mm Grade 2: ≥ 51 to ≤ 100 mm Grade 3: > 100 mm	Grade 1: ≥ 25 to ≤ 50 mm Grade 2: ≥ 51 to ≤ 100 mm Grade 3: > 100 mm

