### 4.4 Derived Endpoints: Calculation Methods

#### 4.4.1 Safety

The solicited period for solicited injection site reactions is from Day (D) 0 to D7 and from D0 to D14 for solicited systemic reactions.

Table 4.1, Table 4.2, and Table 4.3 present, respectively, the injection site reactions and systemic reactions that are prelisted in the DCs and case report form (CRF) for the different age group, together with the intensity scales.

**Table 4.1: Solicited injection site reactions: terminology, definitions, and intensity scales for subjects aged 9 to 11 years**

CRF term (MedDRA lowest level term [LLT])	Injection site pain	Injection site erythema	Injection site swelling
DC term	Pain	Redness	Swelling
Definition		Presence of a redness including the approximate point of needle entry	Swelling at or near the injection site Swelling or edema is caused by a fluid infiltration in tissue or cavity and, depending on the space available for the fluid to disperse, swelling may be either soft (typically) or firm (less typical) to touch and thus can be best described by looking at the size of the swelling
Intensity scale*	Grade 1: Easily tolerated  Grade 2: Sufficiently discomforting to interfere with normal behavior or activities  Grade 3: Incapacitating, unable to perform usual activities	Grade 1: > 0 to < 25 mm  Grade 2: ≥ 25 to < 50 mm  Grade 3: ≥ 50 mm	Grade 1: > 0 to < 25 mm  Grade 2: ≥ 25 to < 50 mm  Grade 3: ≥ 50 mm

\* For the subjective reaction of pain, subjects or parents/legally acceptable representatives recorded the intensity level (Grade 1, 2, or 3) in the DC. For the measurable reactions of redness and swelling, they recorded the size of the reaction and the classification as Grade 1, 2, or 3 will be assigned at the time of the statistical analysis.

**Table 4.2: Solicited injection site reactions: terminology, definitions, and intensity scales for subjects aged  $\geq 12$  years for all subjects**

CRF term (MedDRA LLT)	Injection site pain	Injection site erythema	Injection site swelling
DC term	Pain	Redness	Swelling
Definition		Presence of a redness including the approximate point of needle entry	Swelling at or near the injection site Swelling or edema is caused by a fluid infiltration in tissue or cavity and, depending on the space available for the fluid to disperse, swelling may be either soft (typically) or firm (less typical) to touch and thus can be best described by looking at the size of the swelling

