Intensity scale*	Grade 1: No interference with activity Grade 2: Some interference with activity Grade 3: Significant; prevents daily activity	Grade 1: $\geq 25$ to $\leq 50$ mm Grade 2: $\geq 51$ to $\leq 100$ mm Grade 3: $> 100$ mm	Grade 1: $\geq 25$ to $\leq 50$ mm Grade 2: $\geq 51$ to $\leq 100$ mm Grade 3: $> 100$ mm

\* For the subjective reaction of pain, subjects/parents/legally acceptable representatives recorded the intensity level (Grade 1, 2, or 3) in the DC. For the measurable reactions of redness and swelling, they recorded the size of the reaction and the classification as Grade 1, 2, or 3 will be at the time of the statistical analysis

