##### 4.4.1.1.3 **Presence**

Presence of solicited reactions will be computed based on daily records during the solicited period. For any specific period, a subject would be considered to have a reaction if the intensity is greater than or equal to Grade 1 for at least one day during that period. If no data is recorded and the presence recorded by the Investigator is different from "No", the presence will be considered as "Missing."

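### Erythema and swelling under 25 mm count as a reaction at 9-11 years but not from 12 years, so pooled and by-serostatus rates combine two definitions and can carry an age difference into a serostatus difference

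*SAP*

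**What the plan says.** SAP Table 4.1 sets the scale for erythema and swelling at 9-11 years: "Grade 1: > 0 to < 25 mm", with Grade 3 from 50 mm. For girls of 12 and over, protocol Table 9.2 has "Grade 1: ≥ 25 to ≤ 50 mm", with Grade 3 above 100 mm; SAP Table 4.2 has the same cut-offs. In both age groups the size is recorded and the grade is assigned at analysis.

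SAP 4.4.1.1.3 (Presence) says that a subject is "considered to have a reaction if the intensity is greater than or equal to Grade 1 for at least one day" in the period.

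SAP 5.1.2.2 (Safety) sets the tables: "Safety will be assessed for all subjects and for immune subjects after each and any dose of Cervarix and CYD Dengue vaccine". It then adds that "a complementary analysis will be performed for each dose of CYD dengue vaccine, for each and any group, on non-immune subjects". SAP 5.2.3 and 5.2.5 also call for safety results by baseline dengue status.

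The same part of 5.1.2.2 recognises the scale problem, "As there are differences in the intensity considered for measurable reactions depending on ages of subjects", and plans a complementary analysis at 9-11 and 12-14 years. It does not say that this analysis is done within serostatus, and no common size cut-off is planned. SAP 4.4.4.1 defines age as calendar age without giving a reference date for choosing the scale.

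**The concern.** A 24 mm redness is an event in an 11-year-old and no event in a 12-year-old. A 60 mm redness is Grade 3 in the first girl and Grade 2 in the second. A pooled rate of any, or of Grade 3, erythema or swelling therefore has no single meaning: it depends on how many girls are under 12. Time of onset and number of days of occurrence are derived from the same grades, so they inherit the mixture.

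Randomisation balances age between Group 1 and Group 2 in expectation. It does not do so between immune and non-immune girls, because serostatus is a baseline characteristic. Prior exposure plausibly accumulates with age, so immune girls may be older and more often on the scale with the higher threshold. A reader who sets the immune and non-immune tables side by side could then take a difference in definition for a difference in reactogenicity.

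**Working it through.** The documents give no reaction rate by size and no age distribution by serostatus, so there is no figure of the plan's to reproduce. The check is a mixture calculation on assumed inputs.

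**Taken from the documents:** presence thresholds of > 0 mm (9-11 years) and 25 mm (12 and over); presence requires Grade 1; ages 9 to 14, so both scales are in use.

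**Assumed:** r = P(largest size ≥ 25 mm) and q = P(largest size > 0 but < 25 mm), both equal in all girls whatever their age or serostatus; w = share of girls aged 9-11.

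**Counted rates**
- 9-11 years: r + q
- 12-14 years: r
- ages pooled: r + w × q
- spurious serostatus difference (non-immune minus immune): q × (w_non-immune − w_immune)

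**Effect of the definition alone.** With r = 5% and q = 20%, the counted rate is 25% at 9-11 and 5% at 12-14. With half the girls aged 9-11 the pooled rate is 5 + 0.5 × 20 = 15%. Nothing biological differs between the age groups in this example.

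**Serostatus example.** With the same r and q, and 9-11 shares of 40% (immune) and 60% (non-immune):
- immune: 5 + 0.4 × 20 = 13%
- non-immune: 5 + 0.6 × 20 = 17%
- difference: 4 points, all artefact

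**Range** (spurious difference in percentage points):

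| q | share difference 0 | 10 points | 20 points | 30 points | 40 points |
|---|---|---|---|---|---|
| 5% | 0 | 0.5 | 1.0 | 1.5 | 2.0 |
| 10% | 0 | 1.0 | 2.0 | 3.0 | 4.0 |
| 20% | 0 | 2.0 | 4.0 | 6.0 | 8.0 |
| 30% | 0 | 3.0 | 6.0 | 9.0 | 12.0 |

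**How large might the share difference be?** As an illustration, assume ages uniform over 9-14 and a constant infection hazard, evaluated at mid-ages 10.5 and 13.5.
- At 5% per year the uninfected proportions are exp(−0.525) = 0.592 and exp(−0.675) = 0.509. The 9-11 share is 0.592/1.101 = 54% of non-immune girls and 0.408/0.899 = 45% of immune girls, about 8 points apart.
- At 20% per year they are exp(−2.1) = 0.122 and exp(−2.7) = 0.067. The shares are 65% and 48%, about 16 points apart.

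If any-size erythema is 20% and 50% to 80% of reactions are below 25 mm, q is 10% to 16%. The artefact is then about 0.8 (10% × 8) to 2.6 (16% × 16) points.

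**After a common cut-off.** In the 40% / 60% example, a ≥ 25 mm row reads 5% against 5% and a > 0 mm row reads 25% against 25%. The artefact is zero either way. Comparing serostatus within each age group also gives zero.

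**Grade 3.** The same identity applies, with P(50 mm ≤ largest size ≤ 100 mm) in place of q.

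**The case against.** The strongest reply is that the plan already handles this. The scales are specified in the protocol, the SAP names the difference, and each table of the planned age-group analysis uses one scale. Safety is descriptive, and the safety objective is to describe each vaccine group, not to contrast serostatus groups on local reactions. The concern behind Amendment 1 was hospitalized or severe dengue, not redness. Pain, systemic reactions and SAEs are untouched by the mm cut-offs. The artefact would also be hard to see: if the 480 girls split evenly by serostatus (an assumption), the 95% half-width for 13% against 17% is 1.96 × √(0.13 × 0.87/240 + 0.17 × 0.83/240) = 6.4 points.

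Most of this stands and limits the point to a minor one. It does not remove the mixing from the pooled and by-serostatus rows, and the age split does not resolve a serostatus comparison unless the two are crossed.

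A reader might infer more, and the documents do not support it:

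- **That a false serostatus difference will appear.** This needs a different age mix by serostatus. That is plausible, but the documents give no such data.
- **That the Group 1 against Group 2 comparison is biased.** Age is balanced there in expectation by randomisation.
- **That all the serostatus tables are main tables.** SAP 5.1.2.2 makes the non-immune analysis complementary and limits it to CYD doses.
- **That girls turning 12 change definition between doses.** With uniform ages and dose 3 at about 18 months (12 or 13 months plus a pause of about 6), 1.5/6 = 25% would turn 12 by then. But the SAP's older bracket stops at 14, matching eligibility at inclusion. Under age at each injection, another 25% would pass 15 and fall in neither bracket. Age at inclusion is the more coherent reading, although the SAP does not state it. Dose 3 also cannot affect immune against non-immune, since non-immune girls do not receive it.

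**Conclusion.** The concern holds in a limited form. Pooled and by-serostatus rates of any, and of Grade 3, erythema and swelling combine two definitions; this follows from the text and needs no assumption. Confounding of serostatus with age is conditional. It is 0 if the age mixes are equal, 0 to 12 points over the assumed range, and about 1 to 3 points in the constant-hazard illustration. These sizes assume that true reaction sizes have the same distribution at all ages and in both serostatus groups. The complementary age analysis is a partial remedy. Only descriptive results for two local reactions are affected, so this is a worthwhile small improvement and not a flaw in the trial's conclusions.

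**What to change.** In SAP 5.1.2.2 (Safety), keep the protocol's age-specific grading and do one of the following:

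- add to the all-subject and by-serostatus tables two rows each for erythema and swelling, > 0 mm and ≥ 25 mm, applied to all ages from the recorded sizes; or
- present the 9-11 and 12-14 year tables within each serostatus.

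The first is preferable, because it also gives the all-subject rate a single meaning; the second removes only the serostatus artefact. In either case, state that the scale follows age at V01.

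The cost is a few descriptive rows and no new data. The common-cut-off rates will not equal the sum of the age-specific grades, because a reaction under 25 mm in a girl of 12 or over counts in the > 0 mm row but has no grade. A footnote should say so. For that reason the rows should be added to the protocol's definition and not replace it.

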### 5.1.3 Complementary output

Additional exploratory descriptive analyses based on baseline Zika and FV statuses will be provided in Appendix 15.

- Zika and FV baseline status
- Zika and FV baseline status by baseline dengue status
- Dengue GMTs by Zika and FV baseline status
- Description of immune response to each dengue serotype according to Zika status at baseline

## 5.2 Analysis Sets

Four analysis sets will be used: the Per-Protocol analyses sets (PPX and PPC), the Full Analysis Set (FAS) and the Safety Analysis Set (SafAS).

### 5.2.1 Full Analysis Set

The Full Analysis Set (FAS) is defined as the subset of subjects who received at least one dose of the study vaccine.

Subjects will be analyzed by baseline dengue status and the vaccine treatment group to which they were randomized.

### 5.2.2 Per-Protocol Analysis Set

Two per-protocol analysis sets will be defined: one for Cervarix (PPX) and one for CYD dengue vaccine (PPC). The per-protocol analysis sets are subsets of the FAS.

#### **PPX**

The subjects presenting with at least one of the following relevant protocol deviations will be excluded from the PPX:

- Subject did not meet all protocol-specified inclusion criteria or met at least one of the protocol-specified exclusion criteria
- Subjects identified as dengue non-immune subjects (seronegative) at baseline
- Subject is seropositive at baseline for Cervarix (ie, at least one Ab levels against Cervarix HPV antigens > LLOQ at baseline)
- Subject did not complete the Cervarix vaccination schedule (until V05 for Group 1, V06 for Group 2)
- Subject received a vaccine other than the one that she was randomized to receive (until V05 for Group 1, V06 for Group 2)
- Administration of vaccine was not done as per-protocol (site and route of administration)

- Subject did not receive vaccine in the proper time window (until V05 for Group 1, V06 for Group 2)
- Subject did not provide after the 2nd dose of Cervarix a post-dose serology sample in the proper time window or a post-dose serology sample was not drawn (V05 for Group 1, V06 for Group 2)
- Subject received a protocol-prohibited medication (prohibited therapies/medications/vaccines are indicated in the Protocol Section 6.7) (until V05 for Group 1, V06 for Group 2)
- Subject's serology sample did not produce a valid test result, ie, no Cervarix antigen titer available

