5.1.3 Trial Plan

A summary of the schedule of study vaccination and blood samplings for eligible subjects is provided in [Table 5.1](#).

Table 5.1: Injection and blood sampling schedule by Group

Period	Prior to Amendment 1						Post Amendment 1	
Visit (V)	V01	V02	V03	V04	V05	V06	V07	V08
Timing	D0	M1	M2	M6	M7	M8*	M12 or M13*	M13 or M14*
Group 1†	Cervarix + CYD			Cervarix + CYD			CYD	
	BL	BL			BL			BL
Group 2	Cervarix	CYD		Cervarix	CYD		CYD	
	BL	BL	BL		BL	BL		BL
Subjects not receiving the next CYD‡							Safety follow-up (6 months after the last CYD dengue vaccine injection)	

D: day; M: month; BL: blood sample; CYD: CYD dengue vaccine

* In the original protocol v1.0, subjects from Group 1 were expected to attend V07 at M12 and V08 at M13. Likewise, subjects from Group 2 were expected to attend V07 at M13 and V08 at M14.

At the time of Protocol Amendment 1, procedures planned at V07 (most subjects) or V08 (2 subjects from Group 1) were on hold, depending on subjects' progression. Time for the approval of Protocol Amendment 1 by the competent authorities and completion of the associated logistic tasks will result into a delay of study activities (approximately 6 months), and thus to an extension of study duration for dengue exposed subjects.

† When concomitantly administered, the CYD dengue vaccine and Cervarix will be administered in 2 different sites with the CYD dengue vaccine administered in one deltoid and Cervarix in the other deltoid

‡ This includes seronegative subjects that consent to remain in the study and seropositive subjects that consent to stay in the study but prefer not to receive the next dose of CYD dengue vaccine

At the time of Protocol Amendment 1 writing, all subjects from both groups have received the second injection of CYD dengue vaccine and completed the vaccination schedule for Cervarix. Only 2 subjects from Group 1 had completed the 3-dose schedule for the CYD dengue vaccine. Visits on hold were:

- For Group 1, Visit 7 (M12) was on hold for most of the subjects and Visit 8 (M13) was on hold for the 2 subjects who had received the third dose of CYD dengue vaccine.
- For Group 2, Visit 7 (M13).

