## 5.1 Statistical Methods

In a general way, non-inferiority testing will be performed on dengue immune subjects. The tests will be done only if the number of evaluable subjects provides a global power of at least 80% for the co-primary objectives and secondary objective. In case the global power is insufficient to perform non-inferiority testing, only descriptive analyses will be performed.

Only descriptive analyses will be conducted in dengue non-immune subjects and in the overall population.

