### 5.1.1 Hypotheses and Statistical Methods for Primary Objectives

#### 5.1.1.1 Hypotheses

##### ***Non-inferiority on Cervarix***

The objective is to demonstrate that the humoral immune response to Cervarix administered concomitantly with CYD dengue vaccine is non-inferior to the immune response to Cervarix administered sequentially with CYD dengue vaccine.

Individual hypotheses on Cervarix response for each antigen:

A non-inferiority testing approach will be used to compare geometric mean of titer (GMTs) for the 2 antigens (HPV-16 and HPV-18) 28 days after the last dose of Cervarix, based on the following individual hypotheses:

$$H_0^i: \text{GMT}_{\text{Group1}}^i / \text{GMT}_{\text{Group2}}^i \leq \frac{1}{\delta} \Leftrightarrow \log_{10}(\text{GMT}_{\text{Group1}}^i) - \log_{10}(\text{GMT}_{\text{Group2}}^i) \leq -\log_{10}(\delta)$$

$$H_1^i: \frac{1}{\delta} < \text{GMT}_{\text{Group1}}^i / \text{GMT}_{\text{Group2}}^i > \frac{1}{\delta} \Leftrightarrow \log_{10}(\text{GMT}_{\text{Group1}}^i) - \log_{10}(\text{GMT}_{\text{Group2}}^i) > -\log_{10}(\delta)$$

with:

i, antigen (HPV-16 and HPV-18)

$\delta$  non-inferiority limit is set at 2, ie, 0.301 ( $=\log_{10}[2]$ ), for each antigen "i"

Non-inferiority for antigen i will be demonstrated if the lower bound of the 2-sided 95% CI is greater than  $-\delta$  ( $\alpha=2.5\%$  one-sided).

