### **5.5 Determination of Sample Size and Power Calculation**

A total of 480 subjects will be enrolled: 240 subjects in each group.

The reference standard deviations (SD) considered for Cervarix are 0.4 for both HPV-16 and HPV-18.

The reference seroconversion rates for Cervarix were set to 99% for both antigens.

The reference SD considered are the following for CYD dengue vaccine: 0.9 for serotype 1, 0.7 for serotypes 2 and 3 and 0.5 for serotype 4 (based on CYD13 and CYD15 efficacy studies conducted in subjects aged 9 to 16 years in Latin American countries).

Considering a potential attrition rate of 15%, such sample size would provide 204 evaluable subjects in the per protocol (PP) population per group. This will give, for the co-primary objectives, a global power of 90.2% and for secondary objectives (in terms of Cervarix seroconversion) a power of 91.8%.

Following Protocol Amendment 1, the number of evaluable subjects may be difficult to achieve (considering only dengue immune (seropositive) subjects at baseline to be included in the Per-Protocol populations). Thus the non-inferiority testing will be done only if the number of evaluable subjects provides a global power of at least 80% for the co-primary objectives and secondary objective ie, if the number of evaluable subjects is at least 163 per group for the co-primary objectives and 168 per group for the secondary objective. The power for non-inferiority in terms of GMTs per antigen and serotype is detailed in Table 5.1 and Table 5.3.

This initial study sample size will also provide a 95% probability of observing an AE that has a true incidence of 1.2% in each group (regardless of baseline serostatus).

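### The only planned between-group HPV comparison is confined to dengue-immune subjects; a supportive comparison across both dengue serostatus groups would be a cheap improvement

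*SAP*

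**What the plan says.** - **Analysis set.** SAP 5.2.2 removes from PPX "Subjects identified as dengue non-immune subjects (seronegative) at baseline". SAP 5.2.5 runs the Cervarix non-inferiority tests on PPX only.
- **Everyone else.** SAP 5.1: "Only descriptive analyses will be conducted in dengue non-immune subjects and in the overall population". Under SAP 5.1.2.2 and 5.2.5 this means estimates with 95% CIs within each group, on the FAS and by serostatus. No ratio or difference between groups is specified. The protocol's confirmatory set of exposed subjects (FASE, Protocol 12.2.5) is dropped in SAP 5.7.
- **When tests are run.** SAP 5.5 allows testing only "if the number of evaluable subjects is at least 163 per group for the co-primary objectives and 168 per group for the secondary objective"; otherwise the analysis is descriptive.
- **Timing of the HPV data.** Protocol 5.1.3 reports that when the amendment was written "all subjects from both groups have received the second injection of CYD dengue vaccine and completed the vaccination schedule for Cervarix". The Synopsis adds that all subjects had completed V05 (Group 1) or V06 (Group 2). Protocol 9.1.1.2 places the HPV assay at V01, V02 and V05.
- **Number of exposed subjects.** The Synopsis says this was unknown when the amendment was prepared.

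**The concern.** Amendment 1 withholds the third CYD dose from seronegative subjects. By then both Cervarix doses had been given and the last HPV visit had passed, under the randomized schedule, whatever the subject's dengue serostatus. The randomized HPV comparison could therefore be made in both serostatus groups, but the plan makes it in one. If too few dengue-immune subjects are evaluable, it makes no between-group HPV comparison at all.

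Protocol 1.4 gives the trial's main purpose as showing that the two vaccines can be given together without impairing the response to either. HPV responses in seronegative subjects bear on the Cervarix half of that question. Leaving them out of every between-group estimate loses precision that costs almost nothing to recover.

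**Working it through.** **Inputs (SAP 5.1.1, 5.1.2, 5.5).** One-sided α is 2.5%: "Non-inferiority for antigen i will be demonstrated if the lower bound of the 2-sided 95% CI is greater than" the negative margin. GMT margin: "non-inferiority limit is set at 2, ie, 0.301" on the log10 scale. SDs: "The reference standard deviations (SD) considered for Cervarix are 0.4 for both HPV-16 and HPV-18"; for dengue, "0.9 for serotype 1, 0.7 for serotypes 2 and 3 and 0.5 for serotype 4". Seroconversion is 99% in both groups with a 5-point margin. Enrolment is 240 per group, and 15% attrition leaves 204. Joint power treats endpoints as independent. The seropositive share is not in the documents, so a range is assumed.

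**1. Reproduce the GMT power.** Noncentrality λ = 0.301 / (SD·√(2/n)), with a t test on 2n−2 df.
- n = 204: serotype 1, λ = 3.38, 92.1%; serotypes 2 and 3, λ = 4.34, 99.1% each; serotype 4 and both HPV antigens above 99.9%. Product 90.4% (plan 90.2%).
- n = 163: serotype 1, λ = 3.02, 85.3%; serotypes 2 and 3, 97.2% each. Product 80.6% (plan 80.3%).

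**2. Reproduce the seroconversion power.** The Farrington-Manning score test matches. With restricted rates 0.9946 and 0.9446:
- s0 = √[(0.9946·0.0054 + 0.9446·0.0554)/n], s1 = √[2·0.99·0.01/n], power = Φ[(0.05 − 1.96·s0)/s1].
- n = 204: (0.05 − 1.96·0.01681)/0.00985 = 1.73, so 95.8% per antigen and 0.958² = 91.8% jointly (plan 91.8%).
- n = 168: (0.05 − 1.96·0.01852)/0.01086 = 1.26, so 89.6% and 80.4% (plan 80.4%).

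**3. Power under the planned interval.** The analysis itself uses the Newcombe-Wilson interval. Its power was found by enumerating all outcome pairs at 99% in both arms, summing the probability that the lower bound exceeds −5%, and squaring for two antigens.

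| Seropositive share of 204 (assumed) | n per group | Six-test GMT power | HPV GMT, joint | Seroconversion, joint (Newcombe-Wilson) | Seroconversion, joint (Farrington-Manning) |
|---|---|---|---|---|---|
| 50% | 102 | 48.8% | 99.9% | 37.5% | 35.6% |
| 60% | 122 | 62.0% | >99.9% | 55.1% | 51.7% |
| 70% | 143 | 72.8% | >99.9% | 77.2% | 66.8% |
| 80% | 163 | 80.6% | >99.9% | 81.9% | 78.1% |
| all 204 | 204 | 90.4% | >99.9% | 94.5% | 91.8% |

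The first three rows miss both thresholds. The fourth meets 163 and misses 168. Exact power is saw-toothed in n (76.5% at 150, below the 77.2% at 143), so small steps between rows mean little.

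**4. Share needed to reach the thresholds.** From 204: 163/204 = 80% and 168/204 = 82%. From 240 with no other loss: 163/240 = 68% and 168/240 = 70%.

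**5. What sets each threshold.** The 168 comes from HPV seroconversion alone. The 163 does not come from HPV:
- The two HPV GMT tests reach 80% joint power at n = 38: λ = 0.301/(0.4·√(2/38)) = 3.28, 89.9% each, 80.9% jointly (79.4% at n = 37).
- The four dengue serotypes alone need 162, mainly because of serotype 1 with SD 0.9.

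**The case against.** The strongest reply is that the restriction is deliberate and coherent. The amended protocol defines the Cervarix endpoints in dengue-exposed subjects (9.1.1.1, 9.2.1.1), SAP 5.7 declares the reduced population, and unexposed subjects are no longer to receive CYD. Co-administration is then a question about exposed subjects. This stands as a reason to keep PPX as the main set. Neither document makes the argument for the HPV endpoints specifically, and it does not count against a supportive estimate.

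It can also be said that all-subject HPV results will appear anyway. That is true of the within-group estimates; only the between-group ratio and difference are missing. The gap is real but small.

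A reader might infer more than the documents support:
- *That excluding seronegative subjects threatens the HPV GMT test.* It does not. Power is ample at 102 per group; the risk comes from tying that test to a six-test threshold set by dengue.
- *That the seroconversion test needs an 82% seropositive share.* That assumes exactly 204 evaluable. The 15% attrition was planned for the whole trial, whereas HPV sampling ended at M7 and all subjects reached that visit. With 240 evaluable, the figure is 70%.
- *That every subject has a usable set of HPV samples.* The documents state completed doses and visits. A subject could be vaccinated without a baseline sample (Protocol 5.1.4, Visit 1), and the HPV assay may be skipped when serum is short (9.1.1.1).

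**Conclusion.** The point holds as a cheap improvement; it is not a flaw that invalidates the plan. For seroconversion, restricting the comparison to dengue-immune subjects lowers joint power from 94.5% to about 38–82% over assumed seropositive shares of 50–80% of 204, and the 168 threshold is missed throughout that range. For HPV GMT the loss is not one of power: a co-primary Cervarix test with at least 99.9% joint power at 102 per group can be dropped because dengue titers are variable.

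These figures assume 99% true seroconversion in both arms, independence of the antigens, the plan's SDs and no true difference between groups. The seropositive share is unknown, so loss of the tests is possible but not established. Nor would an all-serostatus comparison restore the formal test in the target population: below the thresholds that test would still not be run.

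**What to change.** Keep PPX and the dengue-exposed target as the main analysis, then:

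- In SAP 5.2.2 and 5.2.5, pre-specify a supportive HPV set: all subjects meeting the other PPX criteria regardless of dengue serostatus, analysed by randomized group with serostatus as a stratum.
- Report the HPV-16 and HPV-18 GMT ratios and seroconversion differences with 95% CIs beside the existing margins, in this set and in PPX, whether or not 163 or 168 is reached. Reporting PPX in every case covers the GMT problem, which widening the set alone would not.
- Declare this in SAP 5.7 as an addition to the descriptive-only rule for the overall population, labelled as supportive. It should be in place before the evaluable counts are known; added after a missed threshold, it would look post hoc.
- Reconcile the sampling visit in the PPX criteria, since the new set inherits it: for Group 2 they name V06 for the sample after the second Cervarix dose, whereas Protocol 9.1.1.2 takes HPV blood at V05 in both groups.

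The cost is a few SAP paragraphs and one table, with no new samples or visits. The downside is that the supportive estimate covers a broader population than dengue-exposed subjects and is not a formal test. Its size may also fall below 204 per group through limited serum or the exclusion of subjects HPV-seropositive at baseline.
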